14.2. Sample Size Justification

The total sample size of 140 subjects who complete the study (Visit 3) was calculated to provide adequate power in detecting statistical superiority of the Test lens relative to prespecified thresholds for binocular distance, intermediate and near logMAR VA, CLUE vision Scores, Absolute toric rotation, rotational stability, rate of unacceptable lens fitting and rate of grade 3 or higher SLFs. All co-primary effectiveness and safety hypotheses are required to achieve statistical significance for the study objective to be satisfied, therefore no adjustment for multiple primary hypotheses is necessary. Each co-primary hypothesis will be tested using a 1-sided Type I error rate of 0.025.

Thresholds for hypotheses associated with CLUE vision, comfort and, handling scores are from a meta-analysis of 14 JJVCI clinical trials of toric and multifocal toric contact lenses used by habitual contact lens wearers aged 40 to 70 years¹². In this analysis, baseline CLUE scores (for subjects' habitual contact lenses) from 14 clinical studies were analyzed to establish thresholds reflecting the "real-world" performance of contact lenses wearers in this population

JJVC CONFIDENTIAL

with respect to CLUE vision, comfort, and handling scores. Thresholds for all other endpoints were based on clinically relevant margins.

Additionally, this study was also powered to test superiority for secondary endpoints with respect to CLUE vision, comfort and, handling scores and lens fit success using a 1-sided Type I error rate of 0.025. Secondary endpoints will be tested using a fixed sequence approach. Further details on the preservation of the study overall Type I error rate are in Section 14.4.

The sample size of 140 to complete yields at least 81% overall power to detect statistical superiority for all co-primary endpoints. This sample size provides a statistical power of at least 99% for each co-primary and secondary endpoint. To account for subject drop-out approximately 155 subjects will be enrolled to ensure at least 140 subjects complete the study.

Endpoint Domain	Endpoint	Statistical Test Type (Statistically Significantly)	Sample Size	Power (%)
Primary Efficacy	Distance (4m) Binocular Visual Acuity (logMAR)	Superiority: mean VA< 0.00	9	99.1
	Intermediate (64cm) Binocular Visual Acuity (logMAR)	Superiority: mean VA< 0.17	6	99.5
	Near (40cm) Binocular Visual Acuity (logMAR)	Superiority: mean VA< 0.17	29	99.1

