Historical data of the Test lens indicates there is a high rate ($\geq 90\%$) for both toric lens rotation $\leq 10^{\circ}$ and rotational lens stability. Assuming a correlation of 0.70 between left and right eyes, a total of 5000 replicating trials were simulated with reference rate of 90.2% for the percentage of eyes with small ($\leq 10^{\circ}$) absolute toric lens rotation (or 99% of eyes with rotational stability). Given the high event rate of the binary outcome, Y=1, each replicated sample was analyzed using a Bayesian beta-binomial model with correlated binary data (Diniz et al; 2010)¹⁴. A non-informative prior distribution, beta (0.5, 0.5) was used to model P_T (proportion of eyes with absolute toric lens rotation $\leq 10^{\circ}$ [or lens stability $\leq 5^{\circ}$] for the Test lens). For each simulated trial, the 95% central posterior credible interval (CrI) constructed for the percentage of eyes with absolute toric lens rotation $\leq 10^{\circ}$ [or lens stability $\leq 5^{\circ}$] for the Test lens was calculated. The null and alternative hypothesis for determining statistical significance in both endpoints were $P_T \leq 80\%$ and $P_T > 80\%$, respectively. With the proposed sample size, each endpoint (percentage of eyes with absolute toric lens rotation $\leq 10^{\circ}$ and lens stability $\leq 5^{\circ}$) has at least 96% power, i.e., 96% of the estimated 95% CrIs had the lower bound above 80%.

Co-Primary Safety Endpoint Sample Size Calculations:

Grade 3 or Higher Slit Lamp Findings (SLF) and Unacceptable Lens Fitting

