Grade 3 or Higher SLFs related to study lens wear was converted to a binary response as Y=1, if a subject eye has a clinically significant SLF, and Y=0 otherwise, for analysis purposes. Historical data show *none or an extremely low rate* (<1%) for clinically significant SLFs (Grade 3 or higher) for the test lens. Assuming a correlation of 0.70 between left and right eyes, a total of 5000 replicating trials were simulated with a reference rate of 1% (worse-case scenario). Given the rare event binary outcome of slit lamp findings, each replicated sample was analyzed using a Bayesian beta-binomial model with correlated binary data (Diniz et al; 2010)¹⁴. A non-informative prior distribution, beta (0.5, 0.5) was used to model P_T (proportion of eyes with Grade 3 or higher SLF for the Test lens). For each simulated trial, the 95% central posterior credible interval constructed for the percentage of eyes with grade 3 or higher SLFs for the Test lens was calculated. The null and alternative hypothesis for statistical significance

were $P_T \ge 5\%$ and $P_T < 5\%$, respectively. With the proposed sample size, at least 99% of the estimated 95% credible intervals had the upper bound below 5%.

As indicated in Table 6, co-primary safety endpoints were powered to at least $\sim 89\%$ individually, yielding a combined power of $\sim 88\%$. With respect to co-primary efficacy, each hypothesis, was powered to $\sim 99\%$, which provided a combined power of $\sim 92\%$. Therefore, the overall combined study power for co-primary safety and co-primary efficacy hypotheses is $\sim 81\%$.

Secondary Efficacy Endpoint Sample Size Calculations:

CLUE Vision, Comfort and, Handling (Hyperopes and Myopes)

Sample size calculations for the secondary endpoints of CLUE vision, comfort, and handling scores were carried out separately for each sphere stratum (hyperopes and Myopes) for all three CLUE domains using one-sided, one-sample mean t-test, with a one-sided Type I error rate of 0.025 for each hypothesis using the *One-Sample T-Tests for Superiority by a Margin* procedure in Power Analysis & Sample Size (PASS2021) software Version 21.0.6 (NCSS LLC, Kaysville UT)¹³. The assumptions for averages and standard deviations were made based on historical values from previous studies (Table 7).

Lens Fit Success

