Absolute toric lens orientation and rotational stability will be analyzed separately using a Bayesian beta-binomial model with correlated binary data¹⁴.

The Model:

Let Y (the percentage of eyes with grade 3 or higher SLFs) be the sum of equicorrelated binary responses (Y_1 and Y_2 denotes left and right eyes, respectively) with probability of success p and correlation coefficient ρ .

The probability distribution of $Y = Y_1 + Y_2$ is obtained by the mixture of two variables. One of them follow a binomial distribution Bin(2, p) with probability of success p and mixing probability $(1 - \rho)$, and the other follows a modified Bernoulli distribution MBern(p), taking values 0 and 2, with probability of success p and mixing probability ρ :

$$P(Y = y | p, \rho) = (1 - \rho) Bin(2, p)I_{A1} + \rho MBern(p)I_{A2}$$

where $I_{A1} = \{0, 1, 2\}$, $I_{A2} = \{0, 2\}$ and *p* is the probability of success (i.e. proportion of eyes with Grade 3 or Higher SLFs).

To overcome the complexity of the mixture likelihood, a latent variable Z_i , i = 1, 2 is introduced in the model to indicate in which component of the correlated binary model the observation y_i , i = 1, 2 belongs to, that is,

$$Z_i = \begin{cases} 1 & \text{if the observation belong to } MBern(p) \\ 0 & \text{if the observation belong to } Bin(2,p) \end{cases}$$

The joint distribution of the augmented data (Y_i, Z_i) , i = 1, 2, is given by

$$\begin{split} P(Y = y_i, Z = z_i | p, \rho) \\ &= \rho^{z_i} \, p^{\frac{y_i z_i}{2}} \, (1-p)^{(2-y_i)\frac{z_i}{2}} \, (1-\rho)^{1-z_i} \, \begin{pmatrix} 2 \\ y_i \end{pmatrix} \, p^{y_i \, (1-z_i)} \, (1-p)^{(2-y_i)(1-z_i)} \end{split}$$

The probability p links to the regression variables through a logit transformation as follow: $logit(p) = \beta_o + \beta_1 lens$

It is assumed that β_o , β_1 and ρ to be independent with a non-informative prior N(0, 1000) for β_o and β_1 , and beta(0.5, 0.5) for ρ . The Metropolis sampler algorithm as implemented in the SAS/STAT MCMC procedure¹¹ will be used to estimate the posterior distributions of the parameters (β_o , β_1 , ρ). Inferences will be made based on a posterior credible interval for the relevant parameters.

The null and alternative hypotheses for evaluating superiority of the Test lens relative to 0.80 for are as follows:

$$H_o: p_T \le 80\%$$

 $H_1: p_T > 80\%$

JJVC CONFIDENTIAL

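### Sections 14.5.1 and 14.5.2: the joint density printed for the four binary co-primaries omits a support indicator, contradicts the mixture above it and, coded as printed, pushes the between-eye correlation towards 1

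*Combined protocol and SAP*

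**What the plan says.** Section 14.5.1 (absolute rotation, rotational stability) and Section 14.5.2 (Grade 3+ slit-lamp findings, unacceptable fit) print the same model. A subject's count Y = Y_1 + Y_2 is Bin(2, p) with weight 1 - rho. With weight rho it is a modified Bernoulli, "taking values 0 and 2", and the mixture carries indicators for the two supports, {0, 1, 2} and {0, 2}.

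A latent Z_i then "is introduced in the model to indicate in which component of the correlated binary model the observation" belongs to, with i = 1, 2. "The joint distribution of the augmented data" follows, and this expression carries neither indicator:

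rho^z * p^(yz/2) * (1-p)^((2-y)z/2) * (1-rho)^(1-z) * C(2,y) * p^(y(1-z)) * (1-p)^((2-y)(1-z))

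The analysis priors are N(0, 1000) on the logit coefficients and beta(0.5, 0.5) on rho. Success is judged on a bound of the 95% central credible interval: lower bound above 80% for the two toric endpoints, upper bound below 5% for slit-lamp findings and below 20% for unacceptable fit. Section 14.2 adds: "Each co-primary hypothesis will be tested using a 1-sided Type I error rate of 0.025".

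**The concern.** Two displayed formulas for the same quantity disagree. The mixture gives an all-or-none pair no chance of discordance; the joint density gives it positive weight. The latent form is introduced to make the mixture easier to handle, so it is the line a programmer is likely to carry into the MCMC procedure.

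Discordant pairs are the main evidence against a high between-eye correlation. If they can be assigned to the all-or-none component, that evidence is reversed. Every co-primary must succeed, so one displaced credible bound on one of these four endpoints could change the trial's conclusion.

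The index adds to the confusion: i = 1, 2 matches the subscripts used for the two eyes, whereas the expression only makes sense with i running over subjects.

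**Working it through.** **Inputs.** From Section 14.2: 140 completers ("The total sample size of 140 subjects who complete the study"); "Assuming a correlation of 0.70 between left and right eyes"; reference rates of 90.2% for rotation, 99% for stability and 1% for slit-lamp findings; a beta(0.5, 0.5) prior on the proportion in the power simulation. From Sections 14.5.1 and 14.5.2: the two formulas, the analysis priors and the success rules. Section 14.2 gives no simulation rate for unacceptable fit, so 1% is assumed.

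**Does the printed density sum to 1?**
- z = 0, all y: (1-rho) times a full binomial = 1 - rho.
- z = 1, y = 0: rho(1-p). z = 1, y = 2: rho*p. Together rho.
- z = 1, y = 1: C(2,1)*rho*p^(1/2)*(1-p)^(1/2) = 2*rho*sqrt(p(1-p)). The mixture requires 0 here.

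Total: 1 + 2*rho*sqrt(p(1-p)). At rho = 0.70 this is 1.139 (p = 0.01 or 0.99), 1.305 (p = 0.05), 1.42 (p = 0.90 or 0.902) and 1.56 (p = 0.80). Without the y = 1, z = 1 cell the total is exactly 1.

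**Direction of the error.** Summed over z, a discordant pair contributes:
- correct: 2(1-rho)p(1-p), which falls as rho rises;
- printed: 2(1-rho)p(1-p) + 2*rho*sqrt(p(1-p)). Its slope in rho is 2[sqrt(p(1-p)) - p(1-p)], which is positive because p(1-p) is at most 1/4.

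At p = 0.902, rho = 0.70: correct 2*0.3*0.0884 = 0.053; printed 0.053 + 0.416 = 0.469.

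**The plan's own power.** Simulation of 5000 trials of 140 pairs, rho = 0.70, beta(0.5, 0.5) on both p and rho:

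| Endpoint (rate) | Correct mixture | As printed |
|---|---|---|
| Slit-lamp (1%) | 88.7% | 88.5% |
| Rotation (90.2%) | 96.4% | 95.0% |
| Stability (99%) | 100% | 100% |
| Unacceptable fit (1%, assumed) | 100% | 100% |

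Table 6 gives 89.3% for slit-lamp findings, which reproduces. Its 96.8% stands on the stability row but matches rotation, so the two toric rows look interchanged. A second run (20,000 trials, normal priors on the logit) gave 96.3% and 94.8% for rotation.

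**Type I error** (5000 trials per setting):

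| Null | rho | Correct | As printed | Correlation ignored |
|---|---|---|---|---|
| Rotation 80% | 0.7 | 2.9% | 1.8% | 7.2% |
| Slit-lamp 5% | 0.7 | 3.1% | 2.3% | 7.4% |
| Rotation 80% | 0.2 | 2.5% | 0.6% | 3.8% |
| Slit-lamp 5% | 0.2 | 1.8% | 0.7% | 3.9% |

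**Single data sets** (subjects with 0/1/2 eyes having the outcome):

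| Data | Correct | As printed |
|---|---|---|
| Rotation 9/8/123, near expectation (a) | 85.7-94.4%, rho 0.65 | 85.2-94.8%, rho 0.98 |
| Rotation 0/27/113 (a) | 86.3-93.3%, rho 0.03 | 84.8-94.5%, rho 0.98 |
| Rotation 12/16/112 (b) | lower bound 80.2%, rho 0.52 | lower bound 79.6%, rho 0.99 |
| Slit-lamp 133/7/0 (b) | upper bound 4.9%, rho 0.10 | upper bound 5.4%, rho 0.95 |
| Slit-lamp 140/0/0 (a) | upper bound 1.33% | upper bound 1.33% |

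(a) beta(0.5, 0.5) on p. (b) The analysis prior, N(0, 1000) read as a variance. The two (b) rows were chosen to sit on the threshold. The slit-lamp reversal also depends on the prior: with beta(0.5, 0.5) on p, that data set fails under both forms.

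**Why the planned effect is small.** The expected number of discordant subjects is 140*2(1-rho)p(1-p): 140*0.053 = 7.4 for rotation, but only 140*2*0.3*0.0099 = 0.8 for stability at 99% or slit-lamp findings at 1%.

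**The case against.** The strongest reply is that the restriction is already in the text. Both sections limit the modified Bernoulli to 0 and 2 and define Z = 1 as membership of that component, so the cell y = 1, z = 1 is excluded by definition. On the remaining z = 1 cells C(2,0) = C(2,2) = 1, and the printed expression is exact. This stands: the fault is a missing indicator, not a wrong model.

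The stated power also points to the right model. Section 14.2 claims at least 96% for each toric endpoint. The correct mixture gives 96.3-96.4% for rotation and the printed form 94.8-95.0%, against a simulation standard error of sqrt(0.964*0.036/5000) = 0.3 points. That is reassuring about the planning program but does not bind the analysis program. The slit-lamp figure cannot tell the two apart. Section 14.1 defers detail to a stand-alone SAP, which is a suitable place for the correction and does not remove the contradiction.

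Two stronger readings are tempting. A reader might infer that the eye correlation is lost and false positives follow. The reverse is true: rho is driven towards 1, and type I error falls rather than reaching the 7.2-7.4% seen when correlation is ignored at rho = 0.7. A reader might also take i = 1, 2 literally as eyes and conclude that the analysis would break down. Y = Y_1 + Y_2, Bin(2, p) and C(2, y) all require a subject-level count, so this is loose notation and no result should be built on it.

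**Conclusion.** Wrong as written, with a modest effect. The printed joint density is not a probability distribution and contradicts the mixture directly above it, for all four binary co-primaries. If it were coded literally, rho would no longer be sensibly estimated once discordant pairs occur. Intervals would generally be too wide and the tests conservative.

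At 140 subjects, rho = 0.70 and the plan's reference rates, rotation loses about 1.5 points of power, slit-lamp findings 0.3 points or less, and stability and unacceptable fit nothing measurable. Type I error did not rise in any setting computed. Only a borderline result could change from pass to fail. With a single discordant subject the slit-lamp upper bound hardly moves (1.64% against 1.63% under the analysis prior), and with none the two forms are identical.

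These sizes assume that the printed line is what gets programmed, which the documents do not establish. The correction should be made before the analysis is run, but the study's validity does not depend on it.

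**What to change.** In Sections 14.5.1 and 14.5.2, replace the joint density with the subject-level probabilities, for subjects i = 1, ..., n and y_i in {0, 1, 2}:

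- P(0) = rho(1-p) + (1-rho)(1-p)^2
- P(1) = 2(1-rho)p(1-p)
- P(2) = rho*p + (1-rho)p^2

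If the latent form is preferred, keep it with the indicator: [rho * p^(y/2) * (1-p)^(1-y/2) * I(y in {0,2})]^z * [(1-rho) * C(2,y) * p^y * (1-p)^(2-y)]^(1-z). A discordant pair then always has z = 0.

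Replace i = 1, 2 with the subject index in both sections. Apply the same specification where Section 14.6 names this model for lens fit success. Before database lock, check the MCMC program against the three probabilities, including a test data set with many discordant pairs: 0/27/113 should return rho near 0.03, not 0.98.

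The cost is a text correction in the protocol or the stand-alone SAP and a short program check. Nothing changes at the sites, in the data collected or in the sample size.

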14.4. Level of Statistical Significance

The Type I error rate of the trial will be controlled at 1-sided 0.025 level. Each co-primary safety and efficacy hypothesis will be tested using a 1-sided Type I error of 0.025. All co-primary hypotheses must be met to satisfy the study objectives and to test any secondary hypotheses.

Based on a gate keeping approach between the primary and secondary families of hypotheses, all primary endpoints must show statistical significance at one-sided 0.025 level in order to pass the full alpha level to test the secondary endpoints hypotheses.

A fixed sequence testing procedure will be utilized to test the secondary hypotheses to control the Type I error rate also in the secondary family of hypotheses. Each secondary hypotheses will be tested using a 1-sided 0.025 level following the order prespecified in section 2.3.3. Based on the fixed sequence principle, each secondary endpoint must be found statistically significant at a one-sided 0.025 level in order to proceed to the next step. If not, the testing procedure of the secondary endpoints will stop.

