where p_T is the percentage of eyes with absolute toric rotation $\leq 10^\circ$ (or lens stability $\leq 5^\circ$) for the investigational lens. Based on Bayesian posterior probability distribution of the proportion p_T , superiority is interpreted as 95% probability of the investigational lens being statistically higher than the threshold of 80% (i.e., $p_T > 80\%$). If the lower bound of the 95% central posterior credible interval is above 80%, it will be concluded that there is 95% probability that the investigational lens is statistically significantly higher than 80% based on observed sample.

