The null and alternative hypotheses for Grade 3 or higher SLFs of the investigational lens compared to the threshold of 5% are as follows:

$$H_o: p_T \ge 5\%$$

 $H_1: p_T < 5\%$

where p_T is the probability of a grade 3 or higher SLF across all study visits for test lens. Based on Bayesian posterior probability distribution of the proportion p_T , superiority is interpreted as 95% probability of test being statistically lower than the threshold of 5% (i.e., $p_T < 5\%$). If the upper bound of the 95% central posterior credible interval is below 5%, it will be concluded that there is 95% probability that the investigational lens is statistically significantly lower than 5% based on observed sample.

Bayesian Estimation and Statistical Evaluation of Hypothesis:

The null and alternative hypotheses for unacceptable lens fitting of the investigational lens compared to the threshold of 20% are as follows:

$$H_o: p_T \ge 20\%$$

 $H_1: p_T < 20\%$

where p_T is the probability of an unacceptable lens fitting across all study visits for test lens. Based on Bayesian posterior probability distribution of the proportion p_T , superiority is interpreted as 95% probability of test being statistically lower than the threshold of 20% (i.e., $p_T < 20\%$). If the upper bound of the 95% central posterior credible interval is below 20%, it will be concluded that there is 95% probability that the investigational lens is statistically significantly lower than 20% based on observed sample.

In the case of zero clinically significant SLF (or unacceptable lens fitting), a Bayesian hierarchical model accounting for zero-event problem will be considered¹⁶.

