The null and alternative hypothesis to test for superiority of the myopic subjects relative to the pre-defined threshold of 51 for the investigational lens is as follows:

$$\begin{array}{l} H_o: \mu_{Myopes} \leq 51 \\ H_A: \mu_{Myopes} > 51 \end{array}$$

Where μ_{Myopes} represents the population mean for the investigational lens after 2-weeks lens wear with respect to CLUE comfort scores for myopic subjects. The investigational lens will be declared statistically significantly greater than 51 if the one-sided p-values is below 0.025.

The null and alternative hypothesis to test for superiority of the myopic subjects relative to the pre-defined threshold of 46 for the investigational lens is as follows:

 $\begin{array}{l} H_o: \mu_{Myopes} \leq 46 \\ H_A: \mu_{Myopes} > 46 \end{array}$

Where μ_{Myopes} represents the population mean for the investigational lens after 2-weeks lens wear with respect to CLUE vision scores for myopic subjects. The Test lens will be declared statistically significantly greater than 46 if the one-sided p-values is below 0.025.

Lens Fit Success (Number of lenses required to achieve lens optimization)

Number of lenses required to achieve lens optimization will be analyzed using a Bayesian betabinomial model with correlated binary data¹⁴.

Bayesian Estimation and Statistical Evaluation of Hypothesis:

Superiority of the Test lens relative to the pre-defined threshold with respect to unacceptable lens fitting will be evaluated using Bayesian statistics. The null and alternative hypotheses for evaluating superiority of the investigational lens relative to 90% are as follows:

$$H_0: p_T \le 90\%$$

 $H_A: p_T > 90\%$,

where p_T is the probability of event (i.e., proportion of subjects to achieve optimization in 4 lenses or less while wearing the test lens). Based on Bayesian posterior probability distribution of the proportion p_T , superiority is interpreted as 95% probability of the Test lens being statistically greater than the pre-defined threshold of 90% (i.e., $p_T > 0.90$) with respect to unacceptable lens fitting rate. If the upper bound of the 95% central posterior credible interval is above 0.90, it can be concluded that there is 95% probability that the investigational lens is superior to the 90% threshold (statistically better) based on the observed sample.

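### For the four co-primary binary endpoints, the definition of superiority as a 95% probability contradicts the interval rule next to it, which requires more than 97.5%

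*Combined protocol and SAP*

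**What the plan says.** Section 14.4 fixes the level: "Each co-primary safety and efficacy hypothesis will be tested using a 1-sided Type I error of 0.025". For the secondary family it says: "Each secondary hypotheses will be tested using a 1-sided 0.025 level following the order prespecified in section 2.3.3".

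Section 14.5.1 covers rotation within 10° and stability within 5°. It gives three statements in a row:

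- a definition: "superiority is interpreted as 95% probability of the investigational lens being statistically higher than the threshold of 80" per cent;
- a test: "If the lower bound of the 95% central posterior credible interval is above 80" per cent;
- a conclusion if the test is met: "it will be concluded that there is 95% probability that the investigational lens is statistically significantly higher than 80" per cent.

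Section 14.5.2 does the same for Grade 3 or higher slit-lamp findings. The definition is "superiority is interpreted as 95% probability of test being statistically lower than the threshold of 5" per cent and the test is "If the upper bound of the 95% central posterior credible interval is below 5" per cent. Unacceptable lens fit follows the same pattern with a 20% threshold.

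Section 14.2 describes the power simulations for rotation, stability and slit-lamp findings. Each counts the share of simulated 95% intervals whose relevant bound clears the threshold.

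Section 14.6 repeats the definition for lens fit success: "superiority is interpreted as 95% probability of the Test lens being statistically greater than the pre-defined threshold of 90" per cent. Its test, however, asks for the upper bound of the interval to be above 0.90.

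**The concern.** A central 95% interval leaves 2.5% of the posterior in each tail. One bound clearing the threshold is therefore a 97.5% criterion, while the sentence before it defines success at 95%. A result with posterior probability between 0.95 and 0.975 would meet the definition and fail the test.

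This matters because every co-primary hypothesis must succeed before the study objective is met and secondary testing opens (Sections 2.3 and 14.4). One such result could decide the trial. Section 14.1 defers detail to a stand-alone SAP, so these sentences are likely to be carried over and programmed. A programmer who worked from the definition would be running roughly a one-sided 0.05 test.

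**Working it through.** **1. What the interval rule requires.** Let L be the lower limit of the central 95% interval, so P(p < L | data) = 0.025. If L > 0.80, then P(p ≤ 0.80 | data) < 0.025, so P(p > 0.80 | data) > 0.975. By the same argument, an upper limit below 5% means P(p < 0.05 | data) > 0.975, and an upper limit below 20% means P(p < 0.20 | data) > 0.975. The tail area of 0.025 is the level set in 14.4. A criterion of P > 0.95 has a tail area of 0.05.

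**2. Which rule was powered.** Inputs from Section 14.2: 140 subjects, correlation 0.70 between eyes, 5000 simulated trials, beta(0.5, 0.5) prior on the proportion. Trials were drawn from the correlated-binomial mixture in 14.5. The correlation was either estimated with a beta(0.5, 0.5) prior or fixed at 0.70; the two results in each cell are in that order.

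| Endpoint | True rate against threshold | P > 0.975 (interval rule) | P > 0.95 | Table 6 |
|---|---|---|---|---|
| Slit-lamp findings | 1% against 5% | 88.6%, 89.6% | 94.3%, 96.7% | 89.3% |
| Rotation | 90.2% against 80% | 96.3%, 97.0% | 98.2%, 98.7% | see below |
| Stability | 99% against 80% | about 100% | about 100% | see below |

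The slit-lamp figure of 89.3% reproduces under the interval rule and not under P > 0.95. The text of 14.2 also claims that at least 99% of slit-lamp intervals lay below 5%. Neither rule gives that, and the next paragraph of 14.2 agrees with Table 6 at about 89%.

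Table 6 prints 96.8% for stability and above 99% for rotation. The inputs suggest that these two entries are interchanged, which is a separate matter. Taken as the rotation figure, 96.8% fits the interval rule better but is too close to 98.2% to settle the question alone.

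**3. False-pass rate at the threshold.** The true rate is set equal to the threshold, with correlation 0.70. The sample is 155 subjects, the enrolment target, because the efficacy analysis is on the ITT population and the safety analysis on the safety population. All outcomes were enumerated. The 80% and 20% thresholds mirror each other, so one line serves rotation, stability and unacceptable fit.

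| Prior | Endpoint | P > 0.975 | P > 0.95 |
|---|---|---|---|
| Sizing prior, beta(0.5, 0.5) on p | 80% (or 20%) threshold | 2.7% | 5.4% |
| Sizing prior | Slit-lamp, 5% | 2.8% | 5.7% |
| Logit prior of 14.5 | 80% (or 20%) threshold | 3.1–3.2% | 6.1% |
| Logit prior of 14.5 | Slit-lamp, 5% | 4.3–4.4% | 7.3% |

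The logit rows read N(0, 1000) as variance 1000 and drop the lens term, since there is only one lens. The ratios are 5.4/2.7 = 2.0, 5.7/2.8 = 2.0, 6.1/3.2 = 1.9 and 7.3/4.4 = 1.7.

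**4. Lens fit success.** An upper limit above 0.90 requires only P(p > 0.90 | data) > 0.025. Treat it as a subject-level binomial with 140 subjects and the beta(1, 1) prior of 14.2. The rule as written then passes with 120 or more successes, and the chance of passing when the true rate is exactly 0.90 is 0.96. With the lower limit, 133 successes are needed and that chance is 0.026. P > 0.95 also needs 133, so in this calculation the bound drives the result and the percentage does not.

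**The case against.** The best answer is that the plan already contains the right test. Both 14.5.1 and 14.5.2 say that inference rests on a posterior credible interval. The conditional sentence is the decision rule, it is the rule that was powered, and it agrees with 14.4. The 95% sentence says only how superiority is interpreted. An analyst would have to set all of this aside to end up testing at 0.05. That stands, and it limits the point to wording.

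Three stronger readings are tempting and are not supported.

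- *The co-primary tests run at one-sided 0.05, or the sample size is wrong.* The stated test is the interval rule, and the slit-lamp power in Table 6 reproduces under it.
- *The report would state a false probability.* When the interval rule is met, the posterior probability exceeds 97.5%, so it also exceeds 95%. The conclusion sentence understates the evidence; it does not err in direction.
- *The same correction serves every binary endpoint.* It does not serve lens fit success, where the rule names the wrong bound.

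It is also fair to say that the wording does not explain all of the excess over 2.5%. The 4.4% for slit-lamp findings arises under the interval rule itself. It comes mainly from the vague logit prior and from discreteness, and changing 95% to 97.5% would leave it where it is.

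**Conclusion.** The contradiction is real. It sits in the success criterion of four co-primary endpoints: toric rotation, rotational stability, Grade 3 or higher slit-lamp findings and unacceptable fit. The 95% definition is the sentence in error, and the interval rule is correct. If the interval rule is followed, nothing changes in the decisions, the power or the number of subjects.

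The exposure is conditional on someone programming the definition. The false-pass rate would then be about twice that of the interval rule with the sizing prior, and up to 7.3% for slit-lamp findings with the logit prior. These rates assume 155 subjects with data, correlation 0.70 between eyes, and the reading of the prior and lens term given above. It should be corrected before database lock, so that a posterior probability between 0.95 and 0.975 leaves no choice to be made after the data are seen.

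**What to change.** In Sections 14.5.1 and 14.5.2, in both the criterion and the conclusion sentence for each of the four endpoints, replace the 95% probability with: *posterior probability greater than 97.5%, equivalent to the relevant bound of the 95% central credible interval clearing the threshold*. Carry the same sentence into the stand-alone SAP.

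In Section 14.6, make the same change for lens fit success only together with a change of the rule from the upper to the lower bound of the interval being above 0.90.

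For the four co-primary endpoints the cost is text only: no new data, no re-sizing, and no change to a program that already uses the interval rule. For lens fit success the change of bound does alter the decision rule as written, and brings it into line with the lower-bound rule simulated in 14.2.
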